6.7.1.1.2 Sustained clinical response

The endpoint of interest is sustained clinical response (i.e., the rate of treatment success of the presenting CDI recurrence and no new CDI episodes for greater than 8 weeks after completing a study treatment). Efficacy assessments will occur at the 4- and 6-month phone assessments.

6.7.1.2 Sensitivity Analysis for the Efficacy Endpoints

The efficacy analyses will be repeated using the ITT and PP population to assess the sensitivity of the endpoints. The ITT analysis will serve as the conservative analysis as it considers all subjects who exit prior to the 8-week efficacy assessment as treatment failures regardless of treatment failure documentation.

Finally, the sensitivity of the efficacy endpoints will be assessed in a multivariate logistic regression adjusting for possible interactions of the following covariates: age (< 65 years, ≥ 65 years), sex (Female, Male), race group (White, Non-white), ethnicity (Hispanic-Latino, not Hispanic-Latino), site geography (outside the US, Eastern US*, Southern US*, Northern US*, Western US*), and categories of number of previous episodes of CDI recurrence at Baseline (≤ 3 , > 3). Comorbidities will also be reviewed for possible interactions. This analysis will be performed on all populations where at least 20 subjects are available in each sub-group.

*States included in the identified US geographical regions are as follows:

- Eastern US: Connecticut, Delaware, District of Columbia, Maine, Maryland, Massachusetts, New Hampshire, New Jersey, New York, Ohio, Pennsylvania, Rhode Island, Vermont, Virginia, West Virginia
- Southern US: Alabama, Arkansas, Georgia, Florida, Kansas, Kentucky, Louisiana, Mississippi, North Carolina, Oklahoma, South Carolina, Tennessee, Texas
- Northern US: Illinois, Indiana, Iowa, Michigan, Minnesota, Missouri, Nebraska, North Dakota, South Dakota, Wisconsin
- Western US: Arizona, California, Colorado, Idaho, Montana, Nevada, New Mexico, Oregon, Utah, Washington, Wyoming

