2.3 Other Objectives

1. To evaluate health-related quality of life in subjects with CDI as measured by the CDI-specific health-related quality of life survey instrument (Cdifff32 questionnaire).
2. To identify Baseline characteristics predictive of efficacy outcomes.
3. To characterize the changes from the Baseline fecal microbial composition at each timepoint.
4. To evaluate the efficacy of a second dose of RBX2660 in preventing CDI recurrence.
5. To assess the clearance of vancomycin resistant enterococcus in subjects who are carriers at Baseline.
6. To assess the clearance of *C. difficile* following enema treatment at 1-week, 4-weeks, 8-weeks, 4-months, and 6-months after study treatment in subjects receiving RBX2660.

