1. **Efficacy Endpoint:** Recurrence of CDI within 8 weeks of treatment.

Recurrence of CDI after 8 weeks from completion of the study treatment is considered a new *C. difficile* infection.

The efficacy parameter used to determine treatment success is defined as the absence of CDI diarrhea through 8 weeks after completing a study treatment. Efficacy assessments will occur at each scheduled office visit: 1-, 4- and 8-weeks.

2. **Efficacy Endpoint:** Loss of sustained clinical response through 6 months after treatment

Sustained clinical response is defined as treatment success of the presenting CDI recurrence and no new CDI episodes through 6 months after completing a study treatment. Efficacy assessments will occur at each scheduled phone assessment: 4 and 6 months.

5.6 **Other Endpoints**

Other endpoints include the following:

1. Baseline characteristics: sex, age, number of prior CDI events, race, ethnicity
2. Subject fecal microbial composition at Screening, 1-week, 4-weeks, 8-weeks, 4 months, and 6 months after study treatment
3. Cdif32 questionnaire at Screening, 1-week, 8-weeks, 4 months, and 6 months

4. Recurrence of CDI within 8 weeks of a second RBX2660 treatment
5. Concentration of vancomycin resistant enterococcus in stool samples for subjects who were carriers at Baseline at 1-week, 4-weeks, 8-weeks, 4 months, and 6 months after study treatment.
6. Presence of *C. difficile* in stool samples at Screening, 1-week, 4-weeks, 8-weeks, 4 months, and 6 months after study treatment

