6.8 Other Endpoints Analyses

Additionally, the other analyses will be conducted on other populations or subgroups as needed.

6.8.1 *Comparison of Baseline characteristics in subjects with treatment success with one dose of RBX2660 vs. those who were unsuccessful.*

A multivariate analysis or regression analysis will be used to identify predictors (if any) for subject success with one RBX2660 dose vs. those who were unsuccessful, for example, age or number of prior CDI events.

6.8.2 *Subject fecal microbial composition at Screening, 1-week, 4-weeks, 8-weeks, 4 months, and 6 months after study treatment.*

Descriptive statistics will be used to present the changes from Screening fecal microbial composition to those at 1-week, 4-weeks, 8-weeks, 4 months, and 6 months after study treatment for those subjects treated with RBX2660.

6.8.3 *Cdiff32 scores at Screening, 1-week, 8-weeks, 4 months, and 6 months.*

Changes from Screening in the Cdiff32 scores will be summarized using descriptive statistics. Last observation carried forward (LOCF) will be used to impute missing post-Baseline data. No inferential statistics will be performed.

6.8.4 *Recurrence of CDI within 8 weeks of second RBX2660 treatment in subjects.*

Determine the treatment success rate of those subjects who received two doses of RBX2660. This success rate will be calculated at 8 weeks following the second RBX2660 enema.

6.8.5 *Concentration of vancomycin-resistant enterococci in stool samples for subjects who were carriers at Baseline.*

Lab generated values for the presence of vancomycin resistant enterococcus based on submitted stool samples at Baseline and at 1-week, 4-weeks, 8-weeks and 4 and 6 months will be assessed for all subjects to identify any trends in the clearance of vancomycin-resistant enterococci following enema treatment.

6.8.6 *Presence of *C. difficile* in stool samples at Screening, 1-week, 4-weeks, 8-weeks, 4 months, and 6 months after study treatment.*

Lab generated values for the presence of *C. difficile* based on submitted stool samples at Baseline and at 1-week, 4-weeks, 8-weeks, 4 months, and 6 months will be assessed for all subjects to identify any trends in the clearance of *C. difficile* following enema treatment.

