7.6 Multi-center Studies and Pooling of Centers

The study will be conducted at up to 80 clinical trial sites in the US and Canada.

This is a multicenter study and before data from all sites are pooled, the effect of site will be assessed for the secondary efficacy endpoints. A sufficient number of subjects (≥ 7) will be

required within each investigative site to determine if there are any outlying sites. If an investigative site is unable to enroll a sufficient number of subjects, it may be necessary to combine smaller sites (where enrollment is too low to detect differences) to create “pseudo-sites”. Sites with < 7 subjects will be considered eligible for pooling. Eligible sites will be pooled sequentially with other sites in the same region until a sufficient number of subjects are reached (at least seven).

In this process, sites with < 7 subjects will be ordered numerically in ascending order, based on the investigative site number. Sites with < 7 subjects will then be sequentially pooled with other sites in the same region in ascending order by site number until the resulting pseudo-site has at least 7 subjects meeting the PP population definition, thus creating a new “pseudo-site”. The process will begin again with the next sequential small site until all small sites have been pooled with other sites in the same region into a pseudo-site.

7.7 **Multiple Comparisons/Multiplicity**

As this study is not powered for a primary objective, and as descriptive statistics will be used for analysis of the primary objective, no adjustments for multiplicity are required.

7.8 **Examination of Subgroups**

Subgroup analysis of age (< 65 years, \geq 65 years), sex (Female, Male), race group (White, Non-white), ethnicity (Hispanic-Latino, not Hispanic-Latino), site geography (outside the US, Eastern US*, Southern US*, Northern US*, Western US*) and number of previous episodes of CDI recurrence at Baseline will be conducted on the efficacy analysis if a sufficient sample size exists for each subgroup. This analysis will include the ITT and mITT analysis populations to understand any differences.

*States included in the identified US geographical regions are as follows:

- Eastern US: Connecticut, Delaware, District of Columbia, Maine, Maryland, Massachusetts, New Hampshire, New Jersey, New York, Ohio, Pennsylvania, Rhode Island, Vermont, Virginia, West Virginia

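### SAP 6.7.1.2 cuts age at 65 and previous recurrences at 3 although both are available on their full scale, and SAP 6.8.1 names the same two predictors without stating a scale

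*SAP*

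**What the plan says.** SAP 6.7.1.2 states that "the sensitivity of the efficacy endpoints will be assessed in a multivariate logistic regression adjusting for possible interactions of the following covariates". The list includes "age (< 65 years, ≥ 65 years), sex (Female, Male", and later "categories of number of previous episodes of CDI recurrence at Baseline", with 3 or fewer set against more than 3. Each of the two variables therefore enters as a single two-level term. No reason is given for either cut.

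Both variables exist on a finer scale. Protocol 10.5 collects date of birth and CDI history, and SAP 6.3 summarizes CDI history by the total number of episodes before treatment.

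Other Objective 2 (SAP 2.3, protocol 6.3) is "To identify Baseline characteristics predictive of efficacy outcomes". The matching item in SAP 5.6 is "Baseline characteristics: sex, age, number of prior CDI events, race, ethnicity". The analysis for it is SAP 6.8.1: "A multivariate analysis or regression analysis will be used to identify predictors (if any) for subject success with one RBX2660 dose". That section offers age and number of prior CDI events as examples and gives no full term list and no scale.

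The age split at 65 also appears in SAP 6.3 (baseline summaries) and SAP 7.8 (subgroups). The split at 3 recurrences appears only in 6.7.1.2; SAP 7.8 lists the number of previous recurrences without categories. SAP 3.3 says that the sample size rests on no power consideration.

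**The concern.** With a cut at 65, a subject aged 66 is treated the same as one aged 90. With a cut at 3, a subject with 4 recurrences is treated the same as one with 10. If risk changes gradually with age or with the number of earlier episodes, the model discards the gradient within each group and keeps only the difference between the groups. A moderate predictor is then estimated less precisely and is more easily missed.

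The same two variables are the named candidates in the predictor analysis, where the coding is left open. In an unblinded single-arm study, an unstated coding can be chosen after outcomes are known, and 6.7.1.2 is the only regression in the SAP that offers a precedent. At stake are the precision and prespecification of a lower-tier objective. The primary safety endpoint and the descriptive secondary efficacy rates are not affected.

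**Working it through.** The plan states no power, effect size or detectable odds ratio, so it has no figure of its own to reproduce. The check asks what a two-group cut costs compared with a continuous term.

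**Inputs from the documents**
- Up to 750 treated subjects (SAP 3.3).
- Treatment success of 70.4% and 78.9% on RBX2660 in two earlier studies (protocol 5.3.4 and 5.3.3).
- 95% confidence level (SAP 7.1), taken here as a two-sided 5% test.

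**Assumptions**
- 700 to 750 evaluable subjects.
- A single predictor, roughly normal, with a log-linear effect.
- The share of subjects on each side of the cut.

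**Step 1: information kept.** With p the share on one side of the cut, c the matching normal quantile and φ the normal density, E = φ(c)² / [p(1−p)].
- 50/50: 0.3989² / 0.25 = 0.637
- 65/35: 0.3704² / 0.2275 = 0.603
- 80/20: 0.2800² / 0.16 = 0.490

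**Step 2: power after the cut.** The noncentrality of the continuous term is 1.960 + z(power). The cut multiplies it by √E, and the new power is Φ(noncentrality × √E − 1.960). For 80% power and a 50/50 split: 2.802 × 0.798 = 2.235, and Φ(0.275) = 60.8%.

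| Split | From 80% power | Loss (points) | From 90% power | Loss (points) |
|---|---|---|---|---|
| 50/50 | 60.8% | 19.2 | 73.4% | 16.6 |
| 65/35 | 58.5% | 21.5 | 71.1% | 18.9 |
| 80/20 | 50.0% | 30.0 | 62.1% | 27.9 |

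**Step 3: fixed sample size.** Noncentrality = ln(OR per SD) × √[N s(1−s)], with s the success rate. For N = 750 and s = 0.75, √(750 × 0.1875) = 11.86. For OR 1.25: 0.2231 × 11.86 = 2.646, so continuous power is Φ(0.686) = 75%. Losses for 50/50 to 65/35 splits:

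| OR per SD | Continuous power | Loss (points) |
|---|---|---|
| 1.10 | 20% | about 6 |
| 1.20 | 58% | 17.3-19.1 |
| 1.25 | 75% | 19.4-21.6 |
| 1.30 | 88% | 17.6-19.9 |
| 1.40 | 98% | 9.0-10.6 |
| 1.50 | 99.8% | 2.8-3.6 |

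At N = 700 with the two earlier success rates and a median split, the loss is 17-19 points at OR 1.25-1.30, 5-6 points at OR 1.10 and 2-6 points at OR 1.50. The small loss at OR 1.50 depends on the sample size: at N = 500 and 80% success it is 12.7-14.8 points.

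**Step 4: simulation for age cut at 65** (N = 750, 75% success, 1,500 runs per setting, assumed mean ages 63 and 68). At OR 1.27 per SD, power falls from 80.0% to 60.9% and from 79.7% to 61.5%. At OR 1.5 it falls from 99.5% to 97.1% in the setting reported. This agrees with the formula.

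**Step 5: count of previous episodes cut at 3.** Here E is the squared correlation between the count and its above-3 indicator. Under assumed Poisson and negative-binomial shapes it is 0.53 to 0.70. The loss is about 15-27 points from 80% power and 13-24 points from 90%.

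**Step 6: the reverse case.** If the true effect is a step exactly at the cut, the two-level term is the correct one. A linear term then falls from 80% to 60.8% (50/50) or 58.5% (65/35).

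**The case against.** The strongest reply is that the cuts sit in a sensitivity regression of the efficacy endpoints, while the predictor objective belongs to SAP 6.8.1, which contains no cut. A number of prior events reads as naturally as a count as it does as a category. This stands. A reader might infer that the plan has already given up 16-22 points of power for its predictor objective, but the SAP never says that 6.8.1 takes over the 6.7.1.2 groups.

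Second, any power figure depends on effect sizes and distributions that the documents do not give, and odds ratios near 1.25-1.30 per SD are about where the loss peaks. This also stands, so the figure is usable only with its conditions. The calculation is for one predictor at a time, whereas 6.7.1.2 describes a multivariable model with interactions.

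Third, power is not a planned property of this study, and no rule is set for declaring a variable non-predictive. That lowers the priority. It does not remove the loss of precision, which affects the confidence interval whether or not a test is made.

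Fourth, a linear term can be the wrong one. That is why the fix includes a non-linearity check.

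A reader might also infer that the cuts bias the other coefficients through residual confounding. There is no treatment coefficient in a single-arm study, and no size has been shown for the remaining ones, so that inference is not made here.

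**Conclusion.** The point holds as a low-priority improvement. In SAP 6.7.1.2 the cuts are definite, unexplained and unnecessary given the data collected. If the predictor is roughly normal with a log-linear effect and the split lies between 50/50 and 65/35, the cut keeps about 60-64% of the information. Power falls by about 17-22 points where the continuous term would have 80-90%.

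Outside those conditions the loss differs. It is about 2-6 points at OR 1.10 or 1.50 per SD with 700-750 evaluable subjects and a near-median split, and about 30 points for an 80/20 split at 80% continuous power. It changes sign for a true step at the cut.

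For the predictor objective itself, what the documents show is an unspecified coding in SAP 6.8.1. The power loss applies there only if that section adopts the 6.7.1.2 categories.

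**What to change.** In SAP 6.7.1.2, replace the two cut terms with age in years and number of previous CDI episodes as continuous terms. Prespecify how non-linearity is checked: a linear term with a stated test of linearity, or a restricted cubic spline. Report odds ratios with 95% confidence intervals. State that SAP 6.8.1 uses the same coding. Because the sections variously refer to recurrences, episodes and events, say which count is meant.

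The under-65 and 65-and-over groups in SAP 6.3 and 7.8 can stay for descriptive display. Neither section contains the split at 3 recurrences, so nothing needs to be changed there on that account.

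The cost is SAP wording, at most one or two extra parameters and a linearity check. No new data are needed.

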6.8 Other Endpoints Analyses

Additionally, the other analyses will be conducted on other populations or subgroups as needed.

6.8.1 *Comparison of Baseline characteristics in subjects with treatment success with one dose of RBX2660 vs. those who were unsuccessful.*

A multivariate analysis or regression analysis will be used to identify predictors (if any) for subject success with one RBX2660 dose vs. those who were unsuccessful, for example, age or number of prior CDI events.

6.8.2 *Subject fecal microbial composition at Screening, 1-week, 4-weeks, 8-weeks, 4 months, and 6 months after study treatment.*

Descriptive statistics will be used to present the changes from Screening fecal microbial composition to those at 1-week, 4-weeks, 8-weeks, 4 months, and 6 months after study treatment for those subjects treated with RBX2660.

6.8.3 *Cdiff32 scores at Screening, 1-week, 8-weeks, 4 months, and 6 months.*

Changes from Screening in the Cdiff32 scores will be summarized using descriptive statistics. Last observation carried forward (LOCF) will be used to impute missing post-Baseline data. No inferential statistics will be performed.

6.8.4 *Recurrence of CDI within 8 weeks of second RBX2660 treatment in subjects.*

Determine the treatment success rate of those subjects who received two doses of RBX2660. This success rate will be calculated at 8 weeks following the second RBX2660 enema.

6.8.5 *Concentration of vancomycin-resistant enterococci in stool samples for subjects who were carriers at Baseline.*

Lab generated values for the presence of vancomycin resistant enterococcus based on submitted stool samples at Baseline and at 1-week, 4-weeks, 8-weeks and 4 and 6 months will be assessed for all subjects to identify any trends in the clearance of vancomycin-resistant enterococci following enema treatment.

6.8.6 *Presence of *C. difficile* in stool samples at Screening, 1-week, 4-weeks, 8-weeks, 4 months, and 6 months after study treatment.*

Lab generated values for the presence of *C. difficile* based on submitted stool samples at Baseline and at 1-week, 4-weeks, 8-weeks, 4 months, and 6 months will be assessed for all subjects to identify any trends in the clearance of *C. difficile* following enema treatment.

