6.7. Other Endpoints

1. Baseline characteristics: sex, age, number of prior CDI events, race, ethnicity
2. Subject fecal microbial composition at Screening, 1-week, 4-weeks, 8-weeks, 4 months, and 6 months after study treatment
3. Cdiff32 questionnaire at Screening, 1-week, 8-weeks, 4 months, and 6 months
4. Recurrence of CDI within 8 weeks of a second RBX2660 treatment
5. Concentration of vancomycin resistant enterococcus in stool samples at Screening, 1-week, 4-weeks, 8-weeks, 4 months, and 6 months after study treatment
6. Presence of *C. difficile* in stool samples at Screening, 1-week, 4-weeks, 8-weeks, 4 months, and 6 months after study treatment

7. Study Design

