7.2. General Study Design

This is an open-label, Phase 3 study to evaluate the safety and tolerability of RBX2660 in subjects with recurrent CDI.

Up to 750 subjects may be treated in this study. Consented subjects who meet all eligibility criteria are intended to be treated. Consented subjects who do not meet the eligibility criteria will be considered screen failures and will not count towards the total number of subjects treated.

Potential subjects are expected to already be taking or have just been prescribed antibiotics to control recurrent CDI symptoms at the time of enrollment (Screening visit)

per the investigator's standard of care. Patients who have already completed their prescribed course of antibiotics to treat recurrent CDI are not eligible for enrollment (Screening visit) unless they have another recurrence that is treated with antibiotics.

Once the Screening visit is complete, in order to proceed to the Baseline Enema Administration:

1. Subject must meet all the inclusion and none of the exclusion criteria
2. Antibiotics will have been administered prior to the washout period
3. CDI symptoms must be under control leading into the antibiotic washout period (**Section 7.3.1**)

Control of CDI symptoms is defined as no longer meeting the symptomatic criteria for CDI diarrhea which is the passage of three or more unformed/loose (i.e., Bristol Stool Scale type 6-7) stools in 24 or fewer consecutive hours while taking antibiotics for the two consecutive days prior to the washout period. Thus, at a minimum the Subject Diary which is started at the Screening visit must show that symptoms are under control the two days prior to the washout period in order for the subject to receive the enema administration.

Study treatment (enema administration) is to be completed as soon as possible, but no later than 21 days after the Screening visit. A minimum of 24hr to a maximum of 72hr antibiotic washout period is required prior to administration of the study treatment.

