10.1. General Information

Study information is collected on study-specific eCRFs by the site. Study monitoring will occur at regular intervals to ensure the protection of subject rights and safety, data integrity and accuracy, and proper study conduct in compliance to the protocol and applicable regulations including 21 CFR 312 and ICH E6 GCPs. Study visits and telephone assessments must occur with the window specified in **Table 10-1**; visits and calls out of window or missed are to be reported as protocol deviations. The study-required procedures are to be conducted as shown in **Table 10-1**.

Timely and complete follow-up visits will ensure the scientific integrity of the data is maintained and allow for continued oversight of subject safety.

Table 10-1 Schedule of Events

Activity	Screening (Enrollment)	Baseline / Enema Administration (≤ 21 days from Screening)	Follow-up Visits: 1- and 8-Week (± 3 days) Assessments ¹	Follow-up Phone Assessment: Week 4 (± 3 days)	Follow-up Phone Assessment: 4 and 6 months (± 14 days)	Unscheduled Possible Recurrence Visit	Second Enema Administration ¹ (≤ 21 calendar days post Tx Failure)	Second Enema Follow-up Phone Assessment: 1-, 4-, and 8-weeks (± 3 days), and 6 months (± 14 days)
Informed consent obtained	X							
Demographics, medical history	X							
Prescribe/continue antibiotics for CDI symptom control	X							
Physical exam	X							
Stool sent to Rebiotix by subjects for testing and archiving (optional)	X		X	X	X	X		X
Central Lab CBC w/differential testing ³	X ³	X						
Central Lab CD4 testing	X ³							
Central Lab CMP & CRP testing	X							
C. difficile testing ⁴						X ⁴		
Central Lab stool and blood testing		X						
Urine pregnancy testing performed at site (if applicable)	X	X					X	
Cdiff32 Questionnaire	X		X		X	X		
Inclusion/exclusion criteria confirmed	X	X						
24-72hr washout period confirmed		X					X ⁷	
Enema administered		X					X	
Product complaint (if applicable)		X					X	
CDI symptoms assessed		X	X	X	X	X	X	X
Vital signs assessed	X	X				X	X	
Weight	X		X	X	X			X
Subject Diary discussed/reviewed	X	X	X ⁵					
Employment status assessed	X		X ⁶		X			
Concomitant medications	X	X	X	X	X	X	X	X
Adverse events assessed		X	X	X	X	X	X	X
Solicited events assessed ²		X	X ²					

¹ Documented treatment failures may receive a second RBX2660 enema.

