Connective Tissue Disease: Yes No

Diabetes Mellitus: Yes No

Type: Type I Type II

End-organ damage: Yes No

Chronic Kidney Disease (Moderate to severe): Yes No

Liver Disease: Yes No

Severity: Mild Moderate Severe

Hypertension: Yes No

Hemiplegia: Yes No

Chronic Pain: Yes No

Dementia: Yes No

Migraines: Yes No

Depression: Yes No

Anxiety: Yes No

Anemia: Yes No

Leukemia: Yes No

Malignant Lymphoma: Yes No

Solid Tumor: Yes No

Metastatic: Yes No

Eczema: Yes No

Acne: Yes No

Psoriasis: Yes No

AIDS/HIV: Yes No

Parkinson's Disease: Yes No

Rheumatoid Arthritis: Yes No

Systemic Lupus Erythematosus: Yes No

Sjogren's Syndrome: Yes No

CREST Syndrome: Yes No

Scleroderma: Yes No

Chronic Urinary Tract Infections: Yes No

Irritable Bowel Syndrome: Yes No

Crohn's Disease: Yes No

Ulcerative Colitis: Yes No

Peptic Ulcer Disease: Yes No

History of Constipation: Yes No

Gastroparesis: Yes No

Gastroesophageal Reflux Disease (GERD): Yes No

Alopecia (hair loss): Yes No

17. Cdiff 32 Health-Related Quality of Life Questionnaire

To be completed by the subject

DAILY ACTIVITIES

Over the last 7 days, because of your *C. diff* infection,

1. Have you had any difficulties and/or disruption carrying out your daily activities?

 1	 2	 3	 4	 5
Not at all	A little bit	Moderately	Quite a bit	Extremely

2. Have you had any difficulties carrying out your leisure activities like gardening, walking, etc?

 1	 2	 3	 4	 5
Not at all	A little bit	Moderately	Quite a bit	Extremely

3. Has it taken you longer to perform certain tasks at work (including work in the home)?

 1	 2	 3	 4	 5
Not at all	A little bit	Moderately	Quite a bit	Extremely

4. Has your *C. diff* infection prevented you from leaving your house?

 1	 2	 3	 4	 5
Never	Rarely	Sometimes	Often	Always

ANXIETY

5. Are you afraid that your *C. diff* infection could come back again?

 1	 2	 3	 4	 5

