5 BASELINE, SAFETY AND EFFICACY EVALUATIONS

5.1 Schedule of Events

Activity	Screening (Enrollment)	Baseline / Enema Administration (≤ 21 days from Screening)	Follow-up Visits: 1- and 8-Week (± 3 days) Assessments ¹	Follow-up Phone Assessment: Week 4 (± 3 days)	Follow-up Phone Assessment: 4 and 6 months (± 14 days)	Unscheduled Possible Recurrence Visit	Second Enema Administration ¹ (≤ 21 calendar days post Tx Failure)	Second Enema Follow-up Phone Assessment: 1-, 4-, and 8-week (± 3 days), and 6 months (± 14 days)
Informed consent obtained	X							
Demographics, medical history	X							
Prescribe/continue antibiotics for CDI symptom control	X							
Physical exam	X							
Stool sent to Rebiotix by subjects for testing and archiving (optional)	X		X	X	X	X		X
Central Lab CBC w/differential testing ³	X ³	X						
Central Lab CD4 testing	X ³							
Central Lab CMP & CRP testing	X							
C. difficile testing ⁴	X ⁴					X ⁴		
Central Lab stool and blood testing		X						
Urine pregnancy testing performed at site (if applicable)	X	X					X	
Cdiff32 Questionnaire	X	X	X		X	X		
Inclusion/exclusion criteria confirmed	X	X						
24-72hr washout period confirmed		X					X ⁷	
Enema administered		X					X	
Product complaint (if applicable)		X					X	
CDI symptoms assessed		X	X	X	X	X	X	X
Vital signs assessed	X	X				X	X	
Weight	X		X	X	X			X
Subject Diary discussed/reviewed	X	X	X ⁵					
Employment status assessed	X		X ⁶		X			
Concomitant medications	X	X	X	X	X	X	X	X
Adverse events assessed		X	X	X	X	X	X	X
Solicited events assessed ²		X	X ²					

¹ Documented treatment failures may receive a second RBX2660 enema.

² Solicited events are collected in the Subject Diary from the day of the baseline enema until the day prior to the 1-week Follow-up visit. The Subject Diary is reviewed at the 1-week Follow-up visit. Solicited events that increase in severity from Screening should be assessed for a possible adverse event.

³ Exclusion criteria for absolute neutrophil count and CD4 should be assessed based on the blood samples collected at the Screening visit.

⁴ Tested at the central laboratory

⁵ Subject Diary is reviewed only at the 1-week Follow-up visit.

⁶ Collected at the 8-week follow-up visit only.

⁷ If antibiotics were administered to manage CDI recurrence.

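### Cdiff32 change from Screening includes improvement on antibiotics before the enema for subjects screened while symptomatic, and only the SAP schedule shows a pre-enema score

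*SAP*

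**What the plan says.** **Reference point.** SAP 6.8.3 states: "Changes from Screening in the Cdiff32 scores will be summarized using descriptive statistics". It adds that missing later scores are carried forward and that no inference is made. The endpoint list in Protocol 6.7 reads "Cdiff32 questionnaire at Screening, 1-week, 8-weeks, 4 months, and 6 months", and SAP 5.6 names the same time points. Neither list has an assessment on the enema day.

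**Schedules.** With empty cells dropped, the row in Protocol Table 10-1 reads "Cdiff32 Questionnaire X X X X" and the row in SAP 5.1 reads "Cdiff32 Questionnaire X X X X X". The additional mark in the SAP is in the Baseline/Enema Administration column. Protocol 10.5 lists the questionnaire at Screening; the pre-administration list in Protocol 10.8 does not contain it. On which schedule sites follow, Protocol 10.1 says: "The study-required procedures are to be conducted as shown in Table 10-1".

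**State at Screening.** Protocol 7.2 expects subjects to "already be taking or have just been prescribed antibiotics to control recurrent CDI symptoms at the time of enrollment (Screening visit"). Inclusion criterion 3 likewise admits subjects who have only just been prescribed treatment. Control of symptoms must be shown in the diary for the two days before a washout of 24 to 72 hours, and the enema must follow within 21 days of Screening.

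**The concern.** The product is studied for preventing recurrence once antibiotics have resolved the episode, so treatment starts from the antibiotic-controlled state. A Screening score describes that state in some subjects and the acute episode in others. Part of the questionnaire makes this distinction sharp: an item such as "Have you had any difficulties and/or disruption carrying out your daily activities" asks about the last 7 days.

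For a subject screened during active CDI, every later change from Screening contains the gain made on antibiotics, in the favourable direction. The study has one open-label arm, so no comparator removes that gain. If no score is taken just before the enema, it cannot be separated afterwards. At stake is how the only quality-of-life comparison in the study will be read.

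**Working it through.** The documents give no planned figure for Cdiff32 to reproduce. The check sets the texts side by side and then does simple arithmetic on time and on an assumed score change.

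**1. Is a pre-enema score required?** Protocol 6.7, Table 10-1 and 10.8 have none, and neither do SAP 5.6 and 6.8.3. Only the SAP 5.1 table shows one. SAP 4.1 reports no change to conduct or analysis, so the extra mark is unexplained, and no SAP analysis uses such a score. This reading does not rest on the table layout alone, because the Protocol 10.5 and 10.8 lists support it.

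**2. Can Screening fall during active CDI?** Yes, mainly for subjects just prescribed antibiotics. Exclusion criterion 2 removes those whose diarrhoea continues despite a course of antibiotics, but not those just starting one.

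**3. How long is the pre-enema period?** The maximum gap is g = 21 days. For a subject just starting antibiotics, the minimum is about 2 control days + 1 day of washout = 3 days.

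**4. Share of the Screening-to-visit interval that precedes the enema.** The formula is g/(g + t), where t is the scheduled study day in SAP 5.2.1 minus 1.

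| Visit | t (days) | g = 3 | g = 21 |
|---|---|---|---|
| 1 week | 7 | 3/10 = 30% | 21/28 = 75% |
| 8 weeks | 56 | 3/59 = 5% | 21/77 = 27% |
| 4 months | 120 | 3/123 = 2% | 21/141 = 15% |
| 6 months | 180 | 3/183 = 2% | 21/201 = 10% |

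With the ±3-day window at week 1 the range is 3/13 = 23% to 21/25 = 84%. With a reference on the enema day the share is 0% at every visit. These are shares of time, not of score change.

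**5. Share of the score change.** Let f be the fraction screened while symptomatic, a their mean improvement before the enema, and b the mean change after it. Taking the pre-enema change of the other subjects as zero, the mean reported change is f·a + b, and the pre-enema part is f·a/(f·a + b). The documents give none of these three quantities, so the values below are assumptions that only show the range.

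| f | a = 10, b = 5 | a = 5, b = 10 |
|---|---|---|
| 0 | 0% | 0% |
| 0.25 | 2.5/7.5 = 33% | 1.25/11.25 = 11% |
| 0.5 | 5/10 = 50% | 2.5/12.5 = 20% |
| 1 | 10/15 = 67% | 5/15 = 33% |

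The result runs from nothing to most of the reported change, depending on inputs that are not available.

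**6. Which items depend on recent state?** In Protocol Section 17, items 1–4, 8, 10–18 and 32 carry a 7-day or past-week recall: 4 + 1 + 9 + 1 = 15 of 32. The other 17 state no recall period.

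**The case against.** The strongest defence is that Screening is a deliberate and openly labelled choice. The endpoint lists and SAP 6.8.3 all name it, SAP 6.3 lets a baseline assessment come from up to 20 days before treatment, and the objective is to evaluate quality of life in subjects with CDI, not to estimate an effect of RBX2660. On this view the mark in SAP 5.1 is a table that was never aligned; the same table also shows a *C. difficile* test at Screening that Table 10-1 lacks. This stands in part. The label is accurate, and change across the whole presenting episode is a legitimate description. It does not make Screening the better reference for the period after the enema, and the schedules conflict whichever is right. For the categorical diary summaries, SAP 6.6.2.5 itself takes the last assessment before the enema as baseline.

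A second defence is that an enema-day score would not isolate the later change cleanly. With a 3-day gap, a 7-day recall on the enema day reaches back before Screening. A week-1 visit on study day 5 also looks back to pre-enema days. More than half of the items state no recall period at all. This is correct and limits the gain, but the enema-day score remains the closer reference.

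A third defence is rank: Cdiff32 is one of the other endpoints, below the primary, secondary and safety endpoints, and is summarised without a test. That also stands, and it limits the importance of the point.

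**Conclusion.** The point holds for subjects screened while symptomatic. Their reported Cdiff32 change includes improvement on antibiotics before RBX2660, by an amount that the documents do not allow to be computed. For subjects already controlled at Screening the extra part is near zero. The conclusion rests on inclusion criterion 3, the late timing of the control requirement, the 21-day limit, and the absence of a pre-enema score from the protocol.

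A reader might infer more, and the documents do not support it:

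- **That antibiotic relief is counted as an RBX2660 effect throughout.** The SAP attributes nothing to RBX2660, and the inflation does not apply to every subject.
- **That no pre-enema score exists.** The protocol requires none, but the SAP schedule shows one and the case report form is not among the documents, so what sites collect is an inference.
- **That a pre-enema reference would give the treatment effect.** In a single open-label arm, change from that score cannot be attributed to RBX2660 either.

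No error rate, safety conclusion or efficacy claim depends on this. It is a worthwhile, low-cost improvement to a descriptive endpoint.

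**What to change.** 1. Reconcile the schedules: add Cdiff32 before the enema to the Baseline column of Protocol Table 10-1 and to the pre-administration list in 10.8, as SAP 5.1 already shows, and align Protocol 6.7.
2. In SAP 5.6 and 6.8.3, make change from the pre-enema score the main summary. Show change from Screening and the Screening-to-Baseline change beside it, so that the antibiotic-phase part is visible.
3. For subjects without a pre-enema score, report change from Screening separately, split by symptom status at Screening (from the CDI history and Subject Diary), and state that it includes the antibiotic period.

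The cost is one 32-item questionnaire at a visit already held, one or two table columns, and a short amendment with the approvals named in Protocol 13.14 across about 80 sites. If enrolment has begun, only later subjects may have the new score, so the reference will be mixed; step 3 deals with that. Reported gains may be smaller.
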